#### 8.1.6 Elevations in ALT or AST, Bilirubin

ALT, AST, total bilirubin, and direct bilirubin will be routinely monitored in this study.

In all cases of elevated ALT, AST, and/or elevated bilirubin (total or direct), possible alternative etiology should be assessed, and the underlying illness treated, or the likely causative agent removed. Sites should counsel participants and their parents/guardians about signs and symptoms of hepatotoxicity. Participants should be advised to notify the study site immediately if they develop any concerning signs or symptoms: new or worsening nausea, vomiting, unexplained loss of appetite; yellowing of the skin or eyes; increased weakness or fatigue; pain in the upper abdomen (liver tenderness or hepatomegaly); pale or clay-colored stools; and/or unexplained weight loss.

Elevated bilirubin in the absence elevated ALT or AST should be managed per Section 8.1.1.

ALT or AST results of severity grade 1 or 2 — other than the grade 2 results specified in the first two bullet points below — require no additional action. Study drug should be continued with routine monitoring per the Schedule of Evaluations unless more frequent monitoring is considered clinically indicated in the opinion of the site investigator. If any results of severity Grade 3 or higher are obtained, all four tests (i.e., ALT, AST, total bilirubin, and direct bilirubin) should be repeated as soon as possible and within three business days. Re-evaluation should continue at least weekly until improvement to grade 2 or lower or until stabilized and no longer in need of frequent monitoring, as determined by the site investigator and in consultation with the CMC.

Study drug must be held in the following scenarios (See Section 7.3.2 for EAE reporting requirements):

- Grade 2 ALT or AST with total bilirubin greater than two times the upper limit of normal (>2xULN) and direct bilirubin greater than 35% of total bilirubin. In this case, study drug should be permanently discontinued, and the CMC should be notified.
- Grade 2 or higher ALT or AST with signs or symptoms of clinical hepatitis (e.g., fatigue, nausea, vomiting, right upper quadrant pain, jaundice) or hypersensitivity (e.g., rash, fever, facial edema, eosinophilia, difficulty breathing). In this case, if another cause of the ALT or AST elevation is identified, consideration may be given to resuming study drug with approval from the CMC.
- Grade 3 ALT or AST for more than two weeks (with total bilirubin ≤2xULN and no signs or symptoms of clinical hepatitis or hypersensitivity). In this case, if another cause of the ALT or AST elevation is identified, consideration may be given to resuming study drug, with approval from the CMC.
- Grade 4 ALT or AST. Hold study drug upon first identification of the Grade 4 result, i.e., pending receipt of the repeat test result; inform the CMC of the initial result and the repeat result. In the case of a confirmed grade 4 result, if another cause of the ALT or AST elevation is identified, consideration may be given to resuming study drug, with approval from the CMC.

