# 6.9 Procedures for Oral Study Product Dispensing and Continued Injectable Study Product Administration

The following procedures must be performed on the same day as and prior to dispensing oral study product or administering a study product injection, to assess for any indication of study product hold or permanent discontinuation:

- Clinical evaluations per the respective scheduled study visit (including participant weight to confirm the appropriate weight-band injectable dosing regimen)
- Laboratory test results from the previous study visit obtained and reviewed for indication of study product hold or permanent discontinuation (see Section 8.4-8.5)
- For participants of childbearing potential, a negative pregnancy test result. For participants of childbearing potential, assessment of contraceptive requirements and use (See Section 6.13)

See Section 8 for details regarding participant management, including additional details related to deferring study product due to managing adverse events and other indications.

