## 7.3.2 EAE Reporting Requirements for this Study

The SAE (serious adverse event) reporting category, as defined in Version 2.0 of the DAIDS EAE Manual, will be used for this study. In addition, the following must also be reported in an expedited manner (i.e., as EAEs), regardless of relationship to study drug:

- Grade 2 or higher ALT or AST with total bilirubin  $\geq 2x$  ULN
- Grade 2 or higher baseline ALT or AST with signs/symptoms of clinical hepatitis
- Grade 3 ALT or AST that persists >2 weeks
- Grade 4 ALT or AST
- Any seizure event

The study agents for which expedited reporting are required are oral cabotegravir (CAB), long-acting injectable cabotegravir (CAB LA), oral rilpivirine (RPV), and long-acting injectable rilpivirine (RPV LA).

Information on adverse events will be included in reports to the US FDA, and other government and regulatory authorities, as applicable.

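### The first liver hold rule in Section 8.1.6 names Grade 2 only, so asymptomatic Grade 3 ALT/AST with the same raised conjugated bilirubin meets no mandatory hold

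*Protocol*

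**What the plan says.** Protocol Section 8.1.6 introduces its compulsory actions with "Study drug must be held in the following scenarios (See Section 7.3.2 for EAE reporting requirements") and gives four bullets:

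1. "Grade 2 ALT or AST with total bilirubin greater than two times the upper limit of normal (>2xULN) and direct bilirubin greater than 35" percent of total bilirubin. Study drug should then be permanently discontinued and the CMC notified.
2. "Grade 2 or higher ALT or AST with signs or symptoms of clinical hepatitis" or of hypersensitivity. Drug is held, but "if another cause of the ALT or AST elevation is identified, consideration may be given to resuming study drug with approval from the CMC".
3. "Grade 3 ALT or AST for more than two weeks (with total bilirubin ≤2xULN and no signs or symptoms of clinical hepatitis or hypersensitivity"). Drug is held, with the same conditional way back.
4. Grade 4 ALT or AST. Drug is held at the first result, before the repeat is known. "In the case of a confirmed grade 4 result, if another cause of the ALT or AST elevation is identified, consideration may be given to" resumption, again with CMC approval.

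For any Grade 3 or higher result the section also asks for ALT, AST, total and direct bilirubin to be repeated within three business days, and for re-evaluation at least weekly with CMC involvement. That instruction contains no hold.

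Section 7.3.2 makes a closely related combination an expedited report regardless of relationship: "Grade 2 or higher ALT or AST with total bilirubin" at or above 2xULN. It has no direct-bilirubin condition.

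Before each dispensing or injection, Section 6.9 requires "Laboratory test results from the previous study visit obtained and reviewed for indication of study product hold or permanent discontinuation", referring to Sections 8.4 and 8.5. Those sections send the reader back to Section 8.1 for holds and stops driven by adverse events, and add criteria that rest on the investigator's judgement.

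**The concern.** A stopping rule should not become weaker as the injury becomes worse. Here the permanent stop is tied to a single grade. Moving from Grade 2 to Grade 3 with unchanged bilirubin and no symptoms takes the child out of the first bullet and into none of the others.

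What is at stake is exposure. Section 1.3.1 describes the injections as a depot that cannot be dialysed or removed, and the participants are aged two to under 12 years. Section 1.2.5 reports drug-induced liver injury in five participants given oral CAB in the Phase I and II programme (under 1%). A site that follows the list literally would find no compulsory reason to withhold the next dose from this child.

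**Working it through.** There is no figure in the plan to reproduce. The check sets the four bullets against one another.

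**Inputs.** The triggers are those of Section 8.1.6. The Grade 2 ceiling for ALT and AST is below 5.0xULN (Sections 4.1.11 and 4.3.2). Fix total bilirubin above 2xULN and direct bilirubin above 35% of total. Vary grade (2, 3, 4) and signs or symptoms (no, yes), which gives 3 × 2 = 6 cells. Bullet 3 cannot apply in any of them, because it requires total bilirubin at or below 2xULN. Duration therefore makes no difference.

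| Grade | Signs or symptoms | Bullets met as written | Listed action | Bullets met with *or higher* in bullet 1 |
|---|---|---|---|---|
| 2 | no | 1 | permanent stop | 1 |
| 2 | yes | 1, 2 | permanent stop, and hold with possible resumption | 1, 2 |
| 3 | no | none | none | 1 |
| 3 | yes | 2 | hold, possible resumption | 1, 2 |
| 4 | no | 4 | hold, possible resumption | 1, 4 |
| 4 | yes | 2, 4 | hold, possible resumption | 1, 2, 4 |

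As written, 2 cells reach the permanent stop, 3 reach only a hold that may be lifted, and 1 reaches nothing. An asymptomatic child at 4.9xULN is directed to stop permanently, while one at 5.0xULN meets no listed hold. A Grade 3 child whose ALT falls to Grade 2 while bilirubin stays high would meet the stop rule only on improving.

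**Is it an omission?** Three places in the protocol suggest so.
- Bullet 3 excludes total bilirubin above 2xULN. That makes sense if Grade 3 with higher bilirubin is dealt with elsewhere, and bullet 1 is the only candidate.
- Section 7.3.2, to which the list's own introduction points, uses Grade 2 or higher for its combination of ALT or AST with bilirubin.
- The screening exclusion in Section 4.2.7 (ALT at least 3xULN, total bilirubin at least 1.5xULN, direct above 35%) has a lower limit for ALT and no upper one.

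The section's lead-in does call the first two bullets Grade 2 results. Since bullet 2 plainly says Grade 2 or higher, that phrase does not show that bullet 1 was meant for Grade 2 alone.

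**Where it bites.** In Cohorts 1 and 2a, Section 4.3.2 requires ALT and AST below 5.0xULN at Week 4a or on repeat, and Section 4.4.2 excludes any related Grade 3 or higher event in Step 1. Persistent Grade 3 at Week 4a therefore blocks the first injection whatever the bilirubin. The exposed doses are mainly the later injections in those cohorts, and Cohort 2b, which has no Step 2 check after entry screening.

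**What remains for the uncovered cell.**

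| Safeguard | Source | Compared with the Grade 2 rule |
|---|---|---|
| Retest within three business days, then at least weekly review | 8.1.6 | no hold |
| Expedited report | 7.3.2 | no hold |
| General rule, if it applies: temporary hold if related, continue if not related | 8.1.1 | resumable, or no hold |
| Deferral or stop on investigator judgement, with the CMC | 8.1.1, 8.4, 8.5 | depends on judgement |

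None of these is the directed permanent stop that Grade 2 receives.

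**After the wording change.** All 6 cells meet bullet 1. Four of them also meet bullet 2, bullet 4 or both, so a permanent stop and a possible resumption then stand side by side. Today this happens in one cell only, symptomatic Grade 2.

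**The case against.** The strongest reply is that a sensible site would not inject this child. Section 8.1.6 says that in every case of raised ALT, AST or bilirubin another cause should be sought and a likely causative agent removed. Section 8.4 requires deferral where the investigator judges dosing unsafe, and Section 8.5 stops drug judged detrimental. Bullet 2 covers signs as well as symptoms, so visible jaundice, fatigue, rash, fever or eosinophilia moves the child into a mandatory hold. Weekly retesting would pick up movement to Grade 4 or back to Grade 2. Section 8.1.1 can be read as a fallback that requires a temporary hold for a related Grade 3 event.

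Much of this stands, and it limits the point. A reader might infer that nothing in the protocol would keep this child from the next injection, or that such a child could pass straight into the injection phase. The documents support neither, given the judgement criteria in Sections 8.4 and 8.5 and the Step 2 limits. The Section 8.1.1 fallback is arguable: it applies to results not listed in the specific sections, and ALT and AST have a section of their own. If it does apply, an event judged not related continues on drug.

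The reply does not remove the inconsistency. The list exists to take certain cases out of individual judgement, and for one of the more serious of them it is silent.

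**Conclusion.** The point holds as a wording defect in a safety rule. One of six combinations with total bilirubin above 2xULN and direct bilirubin above 35%, asymptomatic Grade 3, has no listed hold, while the milder Grade 2 should be permanently discontinued. This rests on reading the four bullets literally and on the child having none of the signs in bullet 2. How often the combination would occur is not stated in the protocol and is not estimated here.

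Two stronger inferences should be resisted. First, a reader might conclude that the permanent stop must override every option to resume. The protocol states no such precedence. Section 1.2.5 attributes the excess of Grade 3/4 ALT in the adult trials to acute viral hepatitis, so removing CMC-approved resumption where another cause is found is a clinical decision. Second, a reader might expect an effect on the safety estimates. An affected child would count as one discontinuation, as any other event would. The interim Safety Guidelines in Section 9.5.2 already count related Grade 3 events, and no sample size or precision figure changes.

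**What to change.** Reword the first bullet of Section 8.1.6 to: *Grade 2 or higher ALT or AST with total bilirubin >2xULN and direct bilirubin >35% of total bilirubin*, leaving its action unchanged.

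At the same time the medical team should decide, and state in one sentence, how this bullet relates to the possible resumption in bullets 2 and 4, since four of the six combinations would then meet both kinds of rule. They may also wish to consider persistent asymptomatic Grade 3 with total bilirubin above 2xULN but direct bilirubin at or below 35%. It meets no bullet now and would meet none after this change.

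The wording change takes a few words in a clarification memo or the next amendment, with no cost in data, visits or sample size. The question of resumption needs a clinical decision but no new data.

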#### 8.1.7 Hypersensitivity Reaction

Hypersensitivity includes a constellation of symptoms such as fatigue, nausea, vomiting, right upper quadrant pain or tenderness, fever, rash, or eosinophilia.

If the IoR or designee suspects hypersensitivity reaction, regardless of relationship to study drug, the participant should be managed as follows:

• Grade 1 or higher: Temporarily hold study product, and within 24 hours of site awareness repeat hematology and chemistries testing on newly obtained samples, and notify the CMC. Continue to re-evaluate the participant, and repeat testing on newly obtained samples at least twice weekly until any abnormal laboratory test results return to baseline values, or stabilize. Refer participant to a specialist or hepatology consultation, at the discretion of the site investigator, and in consultation with the CMC.

## 8.1.8 Allergic Reaction

Participants with allergic reactions should be managed as follows:

- Grade 1 or higher assessed as not related, and Grades 1 or 2 assessed as related: Continue study product, and antihistamines, topical corticosteroids, or antipruritic agents may be prescribed at the discretion of the IoR or designee. The participant should be advised to contact the site immediately if there is any worsening of symptoms or if further systemic signs or symptoms develop.
- **Grade 3 or higher assessed as related:** Permanently discontinue study product, and notify the CMC within 24 hours. Manage as clinically appropriate including antihistamines, topical corticosteroids, or antipruritic agents. Admission to hospital may be required for severe allergic reactions. Following clinical stabilization, re-evaluate the participant weekly, and manage according to standard of care practice at the site until resolution to baseline.

### 8.1.9 Skin Rash

All participants experiencing a rash should be assessed for systemic symptoms, laboratory abnormalities, or mucosal involvement.

Participants with skin rash should be managed as follows, regardless of relationship to study drug:

- Grade 1 (regardless of systemic involvement), or Grade 2 without evidence of systemic involvement: Continue study product use at the discretion of the site investigator.
- Grade 2 with evidence of systemic involvement, or Grade 3 or higher (regardless of systemic involvement): permanently discontinue study product, and consult the CMC within 48 hours. Re-evaluate daily for at least 5 days for systemic symptoms, laboratory abnormalities, mucosal involvement, and for any progression of the rash or increase in severity. Participants may be referred to a dermatologist, at the discretion of the site investigator.

Additionally, for any rash determined to be related to study drug and presenting prior to the Week 4b visit, the CMC must be consulted prior to administering injectable study product at the Week 4b visit.

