## 9.5.2 Safety Guidelines

The Safety Guidelines will consider the adverse event severity, seriousness and attribution to the study drugs. Adverse event attribution to the study drugs will be based on site assessment.

The Safety Guidelines are considered not met, i.e., dose has failed the Safety Guidelines, if:

- at least one participant experienced an adverse event that is fatal or life-threatening and is assessed as related to study drug(s); or
- more than 25% of the participants (e.g., 3 or more of 8 dose-evaluable participants in an interim analysis) experience a Grade 3 or higher adverse event (excluding injection site adverse events, e.g., ISRs) assessed as related to study drug(s) or experience any adverse event assessed as related to study drug(s) that results in permanent discontinuation of the study drug(s).

If none of these conditions are met, then the dose being evaluated has passed the Safety Guidelines.

Given the small sample sizes in a Cohort 1 interim analysis, the information available for safety decisions based on the Safety Guidelines may be imperfect. Two types of sampling errors are possible: 1) if the true rate of toxicity is too high to warrant exposure to the current dose of study drug, the sample data may pass the Safety Guidelines and 2) if the true rate of toxicity is low enough that further exposure to the current dose is warranted, the sample data may fail the Safety Guidelines.

The extent to which the Safety Guidelines protect against the errors described above can be assessed by examining various hypothetical rates of "true toxicity" which could occur if the study drug were used extensively among the participant population at the dose level under question. The hypothetical situations presented in Table 9. (i.e., interim analysis assessment of the Safety Guidelines) range from conditions under which a given dose level would cause a high incidence of severe and life-threatening adverse events to conditions under which severe adverse events would be relatively rare and would not be life-threatening.

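### Sections 8.1.7, 8.1.8 and 8.1.9 overlap for a child with rash and systemic signs and give incompatible study-product instructions, with no rule on which section governs

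*Protocol*

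**What the plan says.** Three neighbouring sections of the protocol govern this presentation.

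- **8.1.7 Hypersensitivity Reaction.** The definition reads: "Hypersensitivity includes a constellation of symptoms such as fatigue, nausea, vomiting, right upper quadrant pain or tenderness, fever, rash, or eosinophilia". The trigger is investigator suspicion: "If the IoR or designee suspects hypersensitivity reaction, regardless of relationship to study drug, the participant should be managed as follows". The only action line is "Grade 1 or higher: Temporarily hold study product, and within 24 hours of site awareness repeat hematology and chemistries testing on newly obtained samples", with notification of the Clinical Management Committee (CMC). The section has no rule for resuming or for stopping permanently.
- **8.1.8 Allergic Reaction.** The term is not defined. For related events of lower grade the text is "Grades 1 or 2 assessed as related: Continue study product", and the same instruction covers unrelated events of any grade. Related events of Grade 3 or higher lead to permanent discontinuation. The section foresees systemic signs developing and asks the participant to contact the site if they do.
- **8.1.9 Skin Rash.** It covers every rash, whatever its relationship to study drug. The lower branch begins "Grade 1 (regardless of systemic involvement), or Grade 2", with the Grade 2 part limited to rash without systemic involvement; there, continuing is left to the investigator's discretion. The upper branch is "Grade 2 with evidence of systemic involvement, or Grade 3 or higher (regardless of systemic involvement): permanently discontinue study product", with CMC consultation within 48 hours.

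Section 8.1.1 supplies general rules only for events not listed in the later sections. It also lets the investigator hold product at any time if continuing would be harmful.

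On the analysis side, Section 9.2 counts a related adverse event of any grade that leads to permanent discontinuation as a drug-related safety failure. Table 4 lists permanent discontinuation due to any adverse event as a separate primary outcome. Section 9.5.2 counts related events causing permanent discontinuation towards its rule that more than 25% of participants fails the dose.

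**The concern.** Rash with constitutional findings is how Section 1.2.5.1 characterises hypersensitivity in the integrase inhibitor class, and rash is listed there separately as a rilpivirine risk. So this is an expected presentation. It meets the 8.1.9 criterion of rash with systemic involvement, it can be suspected hypersensitivity under 8.1.7, and nothing in 8.1.8 stops a site from calling it an allergic reaction.

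Two things are at stake. The first is conduct: a site that obeys one section can breach another, on whether a child stays on a long-acting product whose prolonged exposure, the protocol warns, may complicate management of hypersensitivity. The second is counting: permanent discontinuation is a primary outcome and a component of the drug-related safety failure definition, so for some events the label a site picks decides whether the child is counted.

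**Working it through.** **Step 1. The actions side by side, for rash with systemic signs.**

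| Grade and relationship | 8.1.7 | 8.1.8 | 8.1.9 |
|---|---|---|---|
| Grade 1, related or not | hold | continue | continue, at investigator discretion |
| Grade 2, related or not | hold | continue | permanently discontinue |
| Grade 3 or higher, related | hold | permanently discontinue | permanently discontinue |
| Grade 3 or higher, not related | hold | continue | permanently discontinue |

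Three different actions appear at Grade 2 and at unrelated Grade 3 or higher. At Grade 1, 8.1.9 is permissive, so a hold under 8.1.7 breaches nothing in it; the conflict there is 8.1.7 against 8.1.8. At related Grade 3 or higher, 8.1.8 and 8.1.9 agree and 8.1.7 starts with a hold.

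**Step 2. Is there a precedence rule?** Section 8.1.1 is a fallback for unlisted events, and all three event types are listed. Sections 8.4 and 8.5 refer back to Section 8.1 without ranking its parts. CMC contact is required under 8.1.7 and under the upper branch of 8.1.9, but not under the continue branch of 8.1.8. The CMC check before the Week 4b injection applies only to related rash arising before that visit. None of these says which section governs.

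**Step 3. Effect on the counts.**

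- *Drug-related safety failure (9.2).* Grade 1: no section mandates permanent discontinuation, so the label has no effect. Grade 2, related: counted under 8.1.9; not counted under 8.1.8, nor under 8.1.7 if product is later resumed, unless the event is also a related serious adverse event. Grade 3 or higher, related: counted by grade under any label. Unrelated events: never counted.
- *More than 25% rule (9.5.2).* Same pattern, so only related Grade 2 events depend on the label, and only if the child has no other qualifying event. This rule has no separate component for serious adverse events.
- *Permanent discontinuation due to an adverse event (Table 4).* The label matters at Grade 2 with systemic signs, whatever the relationship, and at Grade 3 or higher: unrelated events differ across all three sections, and related ones differ if 8.1.7 is followed and product is resumed.

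The sensitivity analysis in Section 9.6 re-assesses attribution through the CMC. It does not revisit the action taken, so it does not remove this dependence.

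**Step 4. What one such event would do.** The exact (Clopper-Pearson) 95% limits for x events in n are the 0.025 quantile of Beta(x, n − x + 1) and the 0.975 quantile of Beta(x + 1, n − x).

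- The protocol's own figure (Section 9.4, Table 6): x = 2, n = 50 gives 0.5% to 13.7%, which reproduces the stated 0–14%.
- One more event: x = 3, n = 50 gives 1.3% to 16.5%.
- Interim analysis: 2/8 = 25%, which is not more than 25%; 3/8 = 37.5%, which is.

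These are the shifts that any single extra event causes. They show the leverage of one relabelled related Grade 2 event when two failures are already counted. They do not estimate how often this would happen; the protocol gives no rate for such events.

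**The case against.** The best defence is that the sections have different triggers and can often be followed together. Section 8.1.7 applies only on suspicion of hypersensitivity, 8.1.9 at Grade 1 is discretionary, and a hold under 8.1.7 is a first step that can lead on to discontinuation. The investigator may hold at any time (8.1.1), must defer product for a significant condition that makes dosing unsafe (8.4), and may stop it permanently if it is detrimental (8.5). Section 8.1.6 separately requires a hold when Grade 2 or higher ALT or AST accompanies hypersensitivity signs. The CMC also advises sites on adverse event management generally.

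Most of this stands as mitigation. A reader might infer that a site could be obliged to inject a child whom it believes to be reacting; the general provisions rule that out. A reader might also infer that the label drives the safety failure endpoint at large; Step 3 shows that it does so only for related Grade 2 events. And a reader might infer that the trial's stated precision is lost. The 15% in Section 9.4 is introduced as an example conditional on two failures, not as a design criterion, so a move to 3/50 breaks no commitment.

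What the defence does not answer is Grade 2 with systemic signs, or unrelated Grade 3 or higher. There 8.1.8 says continue and 8.1.9 says stop permanently; no sequence of steps satisfies both, and discretion to hold is not a rule on which one applies.

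**Conclusion.** The point holds as a contradiction in the protocol text. For rash with systemic signs the three sections give three incompatible actions at Grade 2 (any relationship) and at unrelated Grade 3 or higher, and two at Grade 1 (8.1.7 against 8.1.8), with no statement of which governs. The consequence for the child is softened by the investigator's discretion and CMC contact.

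The statistical consequence is real but narrow. The drug-related safety failure endpoint and the Safety Guidelines count are affected only through related Grade 2 events not otherwise counted. The separate primary outcome of permanent discontinuation due to an adverse event is affected more widely, at Grade 2 with systemic signs and at Grade 3 or higher. The numerical shifts are one-event illustrations only.

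This rests on two readings: that a rash with systemic signs can reasonably be given any of the three labels, which the definition in 8.1.7, the lack of one in 8.1.8 and the scope of 8.1.9 all allow; and that a hold under 8.1.7 may end in resumption, which the protocol does not exclude. It matters because these are mandatory stopping instructions for risks that the protocol itself names, in a study whose interim decisions may rest on as few as eight children.

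**What to change.** Reconcile 8.1.7, 8.1.8 and 8.1.9 for rash with systemic signs. Either distinguish the three event types so that a given presentation falls under one section, or state which section prevails when an event fits more than one. Cover at least Grade 2 with systemic involvement, unrelated Grade 3 or higher, and the Grade 1 difference between 8.1.7 and 8.1.8. Which clinical action applies is for the sponsor to choose, and investigator discretion can be kept where it is intended.

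The cost is wording, through a clarification memo or an amendment. It needs no extra visits, tests or participants, and the outcome definitions in Section 9.2 and the Safety Guidelines in Section 9.5.2 can stay as they are.
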